#### **9.1.4 Serious Adverse Device Effects**

A Serious Adverse Device Effect (SADE) is any adverse device effect that has resulted in any of the consequences characteristic of a Serious Adverse Event.

## **9.2 Definition of Hypoglycemia, Hyperglycemia Episodes and Diabetic Ketoacidosis**

Hypoglycemia and hyperglycemia can be symptomatic or asymptomatic and are subset of AEs occurring within Diabetes studies.

Any hypoglycemia or hyperglycemia episode which occurs during the course of the study will be documented by the subject him-/herself in his/her individual Subject Diary, if applicable, or will be defined specifically by the study procedure e.g. in the visit description of this study protocol.

### **9.2.1 Asymptomatic Hypoglycemic Episode**

An asymptomatic hypoglycemic episode is defined as a low blood glucose reading below 70 mg/dL (3.9 mmol/L) without symptoms and is considered as a non-captured expected AE described in Section 9.3.1.2.

### **9.2.2 Symptomatic Hypoglycemia Episode**

A symptomatic hypoglycemia episode is defined as an AE with symptoms consistent with hypoglycemia and may be confirmed by blood glucose readings below 70 mg/dL (3.9 mmol/L).

Symptoms might include but are not limited to: sweating, dizziness, light-headedness, tremors, nervousness, hunger, headaches, weakness or tiredness.

Symptomatic hypoglycemia will be recorded by the subject in their Subject Diary, if applicable, and transferred to the AE Form in the eCRF by the Investigator or authorized site staff and is considered an expected and captured AE, as described in Section 9.3.1.1.

### **9.2.3 Severe Hypoglycemia Episode**

A severe hypoglycemia episode is defined as symptoms in loss of consciousness and/or seizures resolving upon administration of glucose or glucagon by another person (only third-party assistance). A blood glucose value below 36 mg/dL (2.0 mmol/L) might be available, but is not mandatory (if no assistance, then not considered Severe Hypoglycemia).

Such episodes are defined as SAEs and, thus, they must follow the SAE reporting pathway via the eCRF (or be faxed).

### **9.2.4 Hyperglycemic Episode**

Hyperglycemia is defined as high blood glucose readings, a recommended threshold to intervene could be defined as values above 250 mg/dL (13.9 mmol/L). However, investigators should consider the condition of the individual subject.

Only hyperglycemia episodes in combination with medical intervention or additional diagnostic procedures have to be documented as AE in the eCRF, as described in Section 9.3.1.1.

### 9.2.5 Diabetic Ketoacidosis

Diabetic Ketoacidosis is defined as any symptoms such as polydipsia, polyphagia, polyuria, nausea, or vomiting; and presence of serum ketones, or moderate or high urinary ketones; and either arterial blood pH <7.3 or serum bicarbonate <15 mg/L and treated as directed by the subject’s physician.

[figure not shown]
Such episodes are also defined as SAEs and, thus, they must follow the SAE reporting pathway via the eCRF (or be faxed).

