#### 9.3.1 Expected Adverse Events

##### 9.3.1.1 Captured Expected Adverse Events

The following expected AEs may occur at any time in the course of managing diabetes. Immediate or short-term risks to subjects from some of these expected AEs are higher than those identified under Non-Captured Expected AEs.

Therefore, for the purposes of this study, the following expected AEs will be considered captured expected AEs and the AE Form in the eCRF needs to be completed:

- Symptomatic hypoglycemia episodes (see Section 9.2.2).

- Hyperglycemia in combination with medical intervention.
- Hyperglycemia in combination with medical intervention or suspected by the site staff to be caused by insulin leakage or infusion set occlusion.
- Infusion site infection and abscesses, if applicable.
- Unintentional needle stick injury with the guiding needle of the infusion set, if applicable.
- Plaster reactions to the infusion set, if applicable.
- Generalized hypersensitivity reactions.
- Ketosis and ketoacidosis.

These captured expected AEs will be handled as follows:

Subjects will be instructed to follow their personal physicians' instructions for management of low and high blood glucose values or otherwise as instructed by the Investigator.

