## 11.7 Safety Analysis

All AEs will be coded using the Medical Dictionary for Regulatory Activities (MedDRA). Only AEs occurring after the start of the treatment with either MDI, mylife™ Omnipod® or Accu-Chek® Solo micropump system will be included in the AEs tables.

Summaries of incidence rates (frequencies and percentages) of individual AEs by MedDRA System Organ Class and Preferred Term will be prepared. Such summaries will be displayed for all AEs, AEs by maximum severity, AEs by strongest causality to study device (and any associated pump devices), and AEs leading to withdrawal of study device.

Deaths, other SAEs and AEs leading to withdrawal will be listed separately.

In addition, the sub-group of ADEs and SADEs will also be summarized by MedDRA System Organ Class and Preferred Term including summaries by study device.

Episodes (numbers) of the following AEs will be summarized:

- Symptomatic hypoglycemia
- Severe hypoglycemia (SAEs)
- Diabetic Ketoacidosis (SAEs)

The following ADEs are of particular interest:

- ADEs leading to replacement of device.

Incidence rates of all ADEs and of these ADEs and AEs of special interest (as captured on the AE Form in the eCRF) per 100 patient years will be calculated together with exact two-sided 95% CIs assuming that the number of special AEs observed in the study is Poisson distributed.

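### The bicarbonate limit in the DKA definition is printed in mg/L and cannot be met in practice, so DKA may be classified inconsistently and undercounted in one safety line

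*Protocol*

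**What the plan says.** Protocol 9.2.5 builds the DKA definition from three parts joined by *and*:

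- Symptoms: "Diabetic Ketoacidosis is defined as any symptoms such as polydipsia, polyphagia, polyuria, nausea, or vomiting".
- Ketones: "presence of serum ketones, or moderate or high urinary ketones".
- Acidosis: "either arterial blood pH <7.3 or serum bicarbonate <15 mg/L".

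The section then gives the consequence: "Such episodes are also defined as SAEs". Protocol 11.7 and SAP 6.12 both list "Diabetic Ketoacidosis (SAEs" among the episodes to be summarised. The SAP has no DKA definition of its own, so 9.2.5 is the only one available.

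The bicarbonate limit appears nowhere else and has no second unit. The neighbouring glucose limits carry two units, for example "A blood glucose value below 36 mg/dL (2.0 mmol/L) might be available" in 9.2.3 and "values above 250 mg/dL (13.9 mmol/L" in 9.2.4. Separately, Protocol 9.3.1.1 lists "Ketosis and ketoacidosis" as captured expected AEs, with no laboratory limit attached.

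**The concern.** The either/or wording offers two routes to documenting acidosis. If one route is empty because of its unit, the definition is narrower than it looks. The same text decides whether an episode is a DKA, and therefore automatically an SAE, or only a ketosis or ketoacidosis AE.

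Two things are at stake. First, a patient with symptoms, ketones and a low bicarbonate, but no arterial sample, does not meet the definition as printed and could be missing from the DKA line. Second, the study plans 10 to 20 sites in four countries. With only one unit printed, a site has nothing in the protocol to check it against. Some sites may apply the text as it stands, and others may read the number in the unit their laboratory reports.

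**Working it through.** **1. Unit handling elsewhere in the section.** The protocol shows no derivation of the bicarbonate limit, so there is no figure to reproduce. The glucose limits can be checked by dividing mg/dL by 18.016 (physical constant, not in the documents):

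- 36 / 18.016 = 2.00 mmol/L (printed 2.0, 9.2.3)
- 70 / 18.016 = 3.89 mmol/L (printed 3.9, 9.2.1)
- 250 / 18.016 = 13.88 mmol/L (printed 13.9, 9.2.4)

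All three agree, so the problem is confined to the bicarbonate limit.

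**2. Conversion of the limit.** The molar mass of bicarbonate is 1.008 + 12.011 + 3 × 15.999 = 61.016 g/mol (physical constant, not in the documents).

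15 mg/L ÷ 61.016 mg/mmol = 0.246 mmol/L.

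If the mass is taken as sodium bicarbonate (84.007) the result is 0.179, and if taken as carbon dioxide (44.009) it is 0.341. The range is therefore 0.18 to 0.34 mmol/L, and no reading of the mass unit changes the picture.

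**3. Does the second alternative add any cases?** Assume the Henderson-Hasselbalch relation with textbook constants: pH = 6.1 + log10[HCO3 / (0.0307 × pCO2)]. At HCO3 = 0.246 mmol/L:

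| pCO2 (mmHg) | pH |
|---|---|
| 5 | 6.30 |
| 10 | 6.00 |
| 40 | 5.40 |

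A pH of 7.3 at this bicarbonate would need pCO2 = 0.246 / (0.0307 × 10^1.2) = 0.51 mmHg. Any sample below the printed limit would already satisfy the pH alternative by a wide margin, so the bicarbonate alternative contributes nothing.

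**4. Why sites could differ.** This step is for scale only and does not suggest which limit was meant. The same numeral read in mmol/L corresponds to 15 × 61.016 = 915 mg/L, 61 times the printed limit. Under that reading the alternative is not empty: at HCO3 = 15 mmol/L and pCO2 = 25 mmHg, pH = 7.39, above 7.3. A patient with bicarbonate just under that level could be a DKA at one site and not at another.

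**5. Where such a case goes.** Take a patient with symptoms, ketones, low bicarbonate and no arterial pH:

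| Rule | Result under the literal text |
|---|---|
| Protocol 9.2.5 | not DKA |
| Protocol 9.3.1.1 | AE Form still required |
| Protocol 9.1.2 | SAE if there is serious deterioration with in-patient hospitalisation or another listed outcome |
| SAP 6.9 | tabulated with hyperglycaemia-related events likely caused by insulin underdosing |
| DKA line, Protocol 11.7 and SAP 6.12 | may be left out |

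**6. Weight of one case.** Assume 60 subjects per arm, no drop-out and 52 weeks per year.

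- Solo: 60 × 39 + 60 × 13 + 60 × 13 = 3,900 weeks; 3,900 / 52 = 75 patient-years. One case is 100 / 75 = 1.3 per 100 patient-years.
- MDI and OmniPod, each: 60 × 26 = 1,560 weeks; 1,560 / 52 = 30 patient-years. One case is 100 / 30 = 3.3 per 100 patient-years.

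With drop-out the exposure shrinks and these steps become larger.

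**The case against.** The strongest reply is that this is a unit slip that careful investigators would read past, in a definition feeding one descriptive line. Nothing in the documents shows that a site applied it literally or that sites differed. Neither document describes a programmed check of laboratory values against 9.2.5. Under Protocol 9.7 the Study Safety Officer makes a medical assessment of each SAE report. SAP 3.5.5 lets Medical Safety ask for related terms to be pooled. Nor do the documents say whether the DKA line is filled from the 9.2.5 definition or from coded terms; if from coded terms, the count might not move at all. Safety is not a primary endpoint (Protocol 2.2).

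Most of this stands, and it rules out three stronger readings that a reader might infer:

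- *That DKA is confirmed by arterial pH alone.* Only the acidosis part reduces to pH. Symptoms and ketones remain mandatory.
- *That every case documented only by bicarbonate is lost.* The routes in step 5 of the working keep such events in the safety data.
- *That the main pump-specific serious event is undercounted.* Protocol 8.1 lists DKA among the known risks of pump therapy, but adds that subjects face the same risks in routine therapy. It neither ranks DKA first nor treats it as specific to pumps.

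A printing or rendering fault in the unit cannot be wholly excluded, because it appears only once. The correct neighbouring units make that unlikely.

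The objection does not repair the definition. An alternative that cannot be met is wrong as written, in text that triggers SAE reporting, and nothing in the SAP corrects it.

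**Conclusion.** The point holds in a limited form. The printed bicarbonate limit is about 0.25 mmol/L (0.18 to 0.34 across readings of the mass unit) and adds no cases to the pH criterion. The consequence is possible inconsistent classification between sites and a possible undercount in the DKA line, not loss of the events.

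The number of cases affected is unknown: the documents give neither an expected DKA rate nor the share documented without arterial pH. Under full planned exposure, one case is worth about 1.3 per 100 patient-years for Solo and 3.3 for each comparator, so a single reclassification would be visible in a rate by device.

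This rests on the literal text, on standard physical and acid-base constants, and on the DKA line following the 9.2.5 definition. The DTQ analysis and the sample size are untouched. This is a minor correction worth making.

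**What to change.** 1. The sponsor's medical function reconciles the unit and confirms the value in Protocol 9.2.5, preferably showing the units that the sites' laboratories report. No limit is proposed here.
2. SAP 6.12 states the same definition and says whether the DKA line is filled from that definition or from coded terms.
3. At the Data Review Meeting before database closure (SAP 5), recorded ketosis and ketoacidosis AEs are checked against the confirmed definition. Any reclassified case is noted in the report.

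The cost is small but not nil. A protocol change goes through the amendment route in Protocol 12.7, including ethics committee submission. SAP version 1.2 was written in the study's final phase, so a SAP clarification plus the case check may be the more practical route, since a note to sites would do little by then. The check covers only the ketosis and ketoacidosis AEs on file, and needs the sites' source records for pH and bicarbonate where these exist.

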### 9.3 Expectedness Classification of Adverse Events

An AE will be classified as either expected or unexpected (see Figure 5).

For the purpose of this study, expected AEs will be divided into non-captured and captured AEs. These distinctions were made based on the frequency of occurrence, severity of event, and risk to subject. All captured AEs will be documented in the eCRF.

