### **9.3.1.2 Non-Captured Expected Adverse Events**

Non-Captured expected AEs may occur at any time in the normal course of managing diabetes. For the purpose of this study, they will be considered as non-captured expected AEs and will not be documented in the eCRF, these include:

- Asymptomatic hypoglycemia episode (see Section 9.2.1).
- Hyperglycemia without medical intervention.
- Hyperglycemia with a suspected cause other than infusion set leakage or occlusion and without medical intervention.
- In the event of a sore finger, subjects will be advised to avoid taking self-monitoring blood glucose samples from that finger.
- In the event of a mild infection at a lancing site, the study subject will be reminded to wash hands before all blood tests and encouraged to consult their nurse or physician on the management of an infection.
- Minor skin damage due to plaster removal which disappears within a few hours.
- Minor bleeding into the infusion set plaster or into the catheter or tubing, if applicable.
- Mild discomfort by plaster or cannula that may result into replacement decision by the subject.
- Also, both planned ambulant contacts and planned hospitalizations for training purposes will be considered non-captured adverse events.

Since these non-captured expected Adverse Events identified above are common as well as expected and pose minimal immediate risk to the subjects, they will not be tracked and logged as AEs during the course of the study. Investigators may log reports of these non-captured expected AEs as is customary within their practice.

These non-captured expected AEs will be handled as follows:

Subjects will be instructed to follow their personal physicians' instructions for management of low and high blood glucose values as well as for minor skin damage, minor bleeding and mild discomfort.

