### **9.3.2 Unexpected Adverse Events**

All AEs which do not meet the criteria mentioned under expected AEs (Section 9.3.1) are considered as unexpected AEs and will be documented in an AE Form in the eCRF.

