### 6.12. Evaluation of Safety Variables

The safety analysis will be based on the SP and on the device, a subject is using at the time, when a safety event occurs. Since all subjects in treatment arms B and C will receive an Accu-Chek® Solo micropump system at Visit 4 (week 26) and will use it until the end of the study, AEs and SAEs occurring at or after Visit 4 will be attributed to the Accu-Chek® Solo micropump

system. Distinction will be handled and documented according to the description in section 6.2.1.

All AEs will be coded using the Medical Dictionary for Regulatory Activities (MedDRA). Summaries of incidence rates of overall AEs and of individual AEs by MedDRA system Organ Class and Preferred Term will be prepared. Furthermore, summaries will be tabulated for all AEs, AEs by maximum severity, AEs by strongest causality to study device.

Summaries will include number of events, number of subjects affected, the percentages of all subjects for a given treatment, and the events per year of use for a given device.

Defective devices will be tabulated and listed by device type and treatment arm.

Deaths, SAEs and AEs leading to withdrawal will be listed separately.

Episodes (numbers) of the following AEs will be summarized:

- Symptomatic hypoglycemia
- Severe hypoglycemia (SAEs)
- Diabetic Ketoacidosis (SAEs)

The following ADEs are of particular interest:

- ADEs leading to replacement of device.

Incidence rates of all ADEs and of these ADEs and AEs of special interest (as captured on the AE Form in the eCRF) per 100 patient years will be calculated together with exact two-sided 95% CIs assuming that the number of special AEs observed in the study is Poisson distributed.

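### The list of minor events exempt from AE recording covers pump sites but not injection sites, so the by-device AE tables rest on unequal capture rules for minor local events

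*Protocol*

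**What the plan says.** Protocol 9.3 divides expected AEs into captured events, which go on an AE Form, and non-captured events, which do not. It gives the basis for the split: "These distinctions were made based on the frequency of occurrence, severity of event, and risk to subject".

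The non-captured list in 9.3.1.2 has three local items that concern the plaster, cannula or catheter:
- The item on skin damage reads: "Minor skin damage due to plaster removal which disappears within a few hours".
- The item on bleeding reads: "Minor bleeding into the infusion set plaster or into the catheter or tubing, if applicable".
- The item on discomfort reads: "Mild discomfort by plaster or cannula that may result into replacement decision by the subject".

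Two further local items can arise in any arm: a sore finger, and one that begins "In the event of a mild infection at a lancing site". Of the whole group the section says "they will not be tracked and logged as AEs during the course of the study". Neither 9.3.1.1 nor 9.3.1.2 has an item for an injection site.

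Protocol 9.3.2 deals with the remainder: "All AEs which do not meet the criteria mentioned under expected AEs (Section 9.3.1) are considered as unexpected AEs and will be documented" on an AE Form.

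The outputs are in protocol 11.7 and SAP 6.12, which summarise AEs by MedDRA System Organ Class and Preferred Term. SAP 6.12 analyses by the device in use when the event occurs: "Summaries will include number of events, number of subjects affected, the percentages of all subjects for a given treatment", together with events per year of device use.

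**The concern.** A by-device AE table can be read across only if each column was filled under the same recording rule. Here a class of trivial local events is removed by rule from the Solo and OmniPod columns, while nothing removes its counterpart from the MDI column. If sites follow the text as written, the MDI column carries minor injection-site terms whose pump analogues never reach the database as AEs. A reader could take that difference for better local tolerability of the pumps. The study is unblinded (SAP 2.2) and is planned for 10 to 20 sites, so if sites read the gap differently, the recording rule would also vary by site.

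**Working it through.** **1. The recording rule by event, read literally**

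| Minor event | Solo or OmniPod | MDI |
|---|---|---|
| Trivial bleeding at the delivery site | Not recorded (9.3.1.2) | Not listed, so AE Form (9.3.2) |
| Mild discomfort at the delivery site | Not recorded (9.3.1.2) | Not listed, so AE Form (9.3.2) |
| Brief skin damage from plaster removal | Not recorded (9.3.1.2) | No injection-site analogue |
| Sore finger, mild lancing-site infection | Not recorded (9.3.1.2) | Not recorded (9.3.1.2) |
| Delivery-site infection | Recorded (9.3.1.1) | Recorded (9.3.2) |
| Bruising at the delivery site | Not listed, so AE Form (9.3.2) | Not listed, so AE Form (9.3.2) |
| Hyperglycemia without medical intervention | Recorded if leakage or occlusion is suspected (9.3.1.1) | Not recorded (9.3.1.2) |

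The first two rows are the point. The last row runs the other way. In the other rows the arms are treated alike or there is nothing to compare.

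**2. Planned exposure, without dropout**

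Inputs: 60 subjects per arm; 26 weeks on the randomised device; then 13 weeks on Solo for all (protocol outline and 2.1; SAP 2.4).
- MDI: 60 × 26 × 7/365.25 = 29.9 patient-years. OmniPod is the same.
- Solo: (60 × 39 + 120 × 13) × 7/365.25 = 74.7 patient-years.

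**3. Illustration of size**

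The plan gives no AE rates, so there is no figure of its own to reproduce. Every rate below is an assumption, per patient-year, with equal true rates in all arms:
- b = other AEs, recorded in every arm
- m = minor delivery-site events, recorded only on MDI
- h = hyperglycemia without intervention, recorded only on pumps

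Recorded pump/MDI ratio = (b + h)/(b + m). Extra MDI events = m × 29.9.

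With h = 0:

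| m | Extra MDI events | Ratio, b = 1 | Ratio, b = 3 |
|---|---|---|---|
| 0 | 0 | 1.00 | 1.00 |
| 0.1 | 3 | 1/1.1 = 0.91 | 3/3.1 = 0.97 |
| 0.5 | 15 | 1/1.5 = 0.67 | 3/3.5 = 0.86 |
| 1 | 30 | 1/2 = 0.50 | 3/4 = 0.75 |
| 2 | 60 | 1/3 = 0.33 | 3/5 = 0.60 |

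Adding the opposite asymmetry, with b = 1 and m = 0.5:
- h = 0.1: 1.1/1.5 = 0.73
- h = 0.5: 1.5/1.5 = 1.00
- h = 1: 2/1.5 = 1.33
- h = 2: 3/1.5 = 2.00

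The ratio for all AEs together can therefore fall on either side of 1, depending on rates the documents do not give.

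**The case against.** **The text can be read more kindly.** Section 9.3.1.2 presents its list as examples, and its closing instruction mentions minor bleeding and mild discomfort without naming a device. A site could fairly treat a trivial injection-site bleed as non-captured. This shows that the text is ambiguous, but it does not settle the matter. Section 9.3.2 refers to criteria in 9.3.1, whereas frequency, severity and risk are named in 9.3, and the bleeding and discomfort items in 9.3.1.2 are worded for pump sites.

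**A reader might infer that the AE comparison as a whole is biased towards the pumps, and so towards the sponsor's device.** The documents do not support that. Hyperglycemia suspected to come from leakage or occlusion is captured without intervention, which adds events to the pump columns (although 9.2.4 and another item in 9.3.1.2 are narrower, so that rule is itself inconsistent). SAP 3.5.4.1 assigns otherwise unassigned Visit 4 events to Solo. These are different event classes or a single day, so they do not repair the local-site rows, but they leave the overall direction open.

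**A reader might also infer that minor pump-site reactions go wholly unrecorded, or that the split simply follows the device.** Neither holds. Redness, swelling, heat, pain and itching at insertion sites are graded at Visits 2 to 5 and tabulated by group and visit (SAP 6.8.1.4). Among the pump-site items the split does follow severity: infections and plaster reactions are captured, trivial ones are not. Unlisted pump-site events such as bruising reach the AE Form as well. The examinations do not close the gap, because they show only what is present at a visit, omit bleeding, and are described in SAP 4.2.1.5 as concerning the pump insertion site.

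**The practical effect may be nil.** There is no study diary, visits are about 13 weeks apart, and MDI subjects have at least 6 months of experience with injections. They may never mention such events. This stands.

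**Conclusion.** The point holds in a narrow form. Read literally, protocol 9.3.1.2 and 9.3.2 together record trivial bleeding or discomfort at an injection site as an unexpected AE on MDI and leave the pump-site analogue off the AE Form. For minor local-site events, the by-device AE tables therefore rest on unequal capture.

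The size cannot be derived from the documents. The illustration runs from no effect to a recorded ratio of 0.33, entirely on assumed rates and with the opposing hyperglycemia rule left out. Net bias in overall AE counts is not established in either direction.

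The consequence is limited. The AE tables are descriptive, SAP 6.1 rules out testing that is not specified, and safety is not a primary endpoint (protocol 2.2). The DTQ analysis and the SAE listings are unaffected. The correction is worth making because it is nearly free and equalises recording for the events concerned.

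**What to change.** **Protocol 9.3.1.2.** Make the local items device-neutral by adding minor bleeding or mild discomfort at an injection site. This helps only recording still to come. SAP 6.13.1 places the study in its final phase, so the SAP change probably matters more.

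**SAP 6.12, for data already collected.**
- Pre-specify a list of terms, restricted to minor events, for local events that have a non-captured pump analogue: bleeding and discomfort at the delivery site. Apply it in every arm.
- Show the cross-device AE tables with and without those events.
- Keep in the main table everything that 9.3.1.1 requires to be captured, including plaster reactions and site infections. A blanket exclusion of minor local events would remove some of these, possibly in favour of the pumps.
- Footnote the tables with the unequal capture rule, since pump events that were never logged cannot be recovered.

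A list fixed in advance is safer than a review blinded to arm, because a term that names an injection or infusion site reveals the device.

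**Cost.** One line in the protocol, a short paragraph and a term list in the SAP, and one extra table. A few trivial MDI events would no longer be recorded.
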